Traditional measures of response in AML rely on the morphological characterization of blasts after therapy with complete remissions requiring less than 5% blasts to be present in the bone marrow. The morphological determination of blasts lacks sensitivity to identify low levels of residual disease and is subject to both sampling and interpretation error. Measurable residual disease (MRD) denotes the presence of leukemia cells down to levels of  $1:10^4$  to  $1:10^6$  white blood cells (WBCs), compared with 1:20 in morphology-based assessments. Multiple studies have demonstrated that the achievement of a negative MRD status is associated with improved clinical outcomes. In this study, we will utilize a flow cytometry-based MRD assessment at the end of induction and consolidation to explore potential differences in the experimental and control arms and correlate these results with clinical outcomes.

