#### 14.3.4 Statistical Analysis Plan

A041701 is a randomized Phase II/III study. The study will open with accrual open to two arms (one experimental arm and one control arm). The total Phase II sample size is

expected to be approximately 262 eligible patients (131 patients per arm). The total Phase III sample size is expected to be 670 (335 patients per arm). In the event that the Alliance Data Safety and Monitoring Board (DSMB) releases the requested Phase II data, the hypothesis-generating analyses described here will be performed based on Phase II accrual. Otherwise, this proposal is mainly based on Phase III accrual. Because this substudy is being newly incorporated in a protocol amendment post-study activation (54 patients accrued as of 11/22/2019), the current accrual rate suggests that approximately 600 evaluable Phase III patients may participate in this substudy.

We assume that 60% patients treated on A041701 will achieve a CR/CRi. Of those achieving CR/CRi, we expect to have end-of-induction marrow samples for MRD assessment on 90% of patients (n=324), and blood samples on 95% of patients (n=342).

We note that the Cox regression models below will be stratified by treatment arm as appropriate. Multivariable analyses will be evaluated as a complement to each univariate analysis. Multivariable analyses will include baseline covariates age, gender, performance status, cytogenetic risk, white blood cell count, platelet count, bone marrow blast percentage, and number of induction courses (1 vs 2).

*1. Primary integrated objective (To evaluate whether the presence of MRD will be a strong predictor of relapse-free survival (RFS) in patients achieving a CR/CRi following induction chemotherapy):*

We expect that approximately 25% of patients who achieve a CR/CRi will have detectable MRD by flow cytometry using the current methodology. Log-rank test will be used to assess associations between MRD and RFS. And RFS will be estimated by the Kaplan-Meier method.

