In the calculations below, the RFS is assumed to follow an exponential distribution with a median of 11.5 months (null hypothesis). For the RFS outcome (assuming 59 months of accrual and an additional one year of follow-up per protocol), the marrow results (n=324) will have 80% power to detect an absolute difference in median RFS of 5 months between MRD- and MRD+ patients (HR = 0.7), 13 months for MRD- versus 8 months for MRD+ with a two-sided alpha of 0.05, and the blood (n=342) results will have 83% power for the same effect size and alpha level. C-statistics will be calculated to quantify the model's ability to predict outcomes. We will also fit multivariable Cox regression models with both end-of-induction MRD (present vs absent) plus the covariates listed above.

In the event that the Alliance Data Safety and Monitoring Board (DSMB) releases the requested Phase II data, the hypothesis-generating analyses described here will be performed based on Phase II accrual. Similarly, because this substudy is being newly incorporated in a protocol amendment post-study activation (54 patients accrued as of 11/22/2019), the current accrual rate suggests that approximately 200 evaluable Phase II patients may participate in this substudy.

For the RFS outcome (assuming additional 18 months of accrual and an additional one year of follow-up per protocol), the marrow results (n=108) will have 63% power, and the blood (n=114) results will have 65% power for a HR of 0.6 and two-sided alpha of 0.05. C-statistics will be calculated to quantify the model's ability to predict outcomes. We will also fit multivariable Cox regression models with both end-of-induction MRD (present vs absent) plus the covariates listed above.

*To analyze the association of MRD with overall survival (OS), time-to-relapse (TTR, defined as the time from randomization to relapse, with death without relapse censored at time of death), and relapse risk: OS and TTR will be estimated using the Kaplan-Meier*

method, and compared using log-rank tests. Risk of relapse (RR) will be summarized using cumulative incidence estimates. Cox regression analyses will be used to assess the association between the outcomes of interest and the covariates listed above.

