*To compare whether evaluate whether MRD from the peripheral blood provides similar prognostic information compared to bone marrow:* We will fit multivariate marginal Cox regression models (Wei, Lin, Weissfeld 1989) including either blood and marrow MRD results with covariates for sample type (blood versus marrow), and a second model both blood and marrow MRD, and a third model with the interaction between the two covariates. We will calculate C-statistics for each of these models.

*To compare the presence of MRD at the end of induction versus end of consolidation time points to determine if either of these better predicts RFS:* We will fit multivariate marginal Cox regression models (Wei, Lin, Weissfeld 1989) including either MRD results at the end of induction or at the end of consolidation. We will calculate C-statistics for each of these models.

*To compare the rates of MRD by treatment arm:* Two-way table and chi-square tests will be used to compare the MRD rates by treatment arm.

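### The MRD comparison by arm states no denominator and is most likely made among CR/CRi patients only, a group formed after randomization, so its estimate can be biased

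*Combined protocol and SAP*

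**What the plan says.** Section 14.3.1 gives the purpose of the flow cytometry MRD assessment at the end of induction and of consolidation: "to explore potential differences in the experimental and control arms and correlate these results with clinical outcomes". Section 14.3.4 carries out the arm part in one sentence: "Two-way table and chi-square tests will be used to compare the MRD rates by treatment arm". That sentence names no denominator and no time point. It has no rule for patients without remission and none for patients without a sample.

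The only MRD population described in 14.3.4 is patients in remission:
- The CR/CRi rate is taken as 60%, with no split by arm.
- Marrow is then counted within that group: "Of those achieving CR/CRi, we expect to have end-of-induction marrow samples for MRD assessment on 90% of patients (n=324"; blood is expected from 95% of them, or 342.
- "We expect that approximately 25% of patients who achieve a CR/CRi will have detectable MRD by flow cytometry".
- The section's primary integrated objective, MRD as a predictor of relapse-free survival, is set in patients achieving CR/CRi.

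Specimen collection is wider. Section 6.2 and the specimen text in 14.3.3 schedule end-of-induction marrow for LC1 patients without limiting it to remission. Under section 4.6.1, patients are registered to LC1 at the same time as to the treatment trial.

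**The concern.** CR/CRi is reached after randomization, and section 1.5 names higher than expected CR/CRi rates as a reason for the trial. If the drug works as hoped, the responders in the two arms are no longer comparable groups. The experimental arm would contain extra responders who would have failed on 7+3 alone. If those patients carry residual disease more often than other responders, they raise the MRD-positive rate on uproleselan while their own outcome has improved. A chi-square test on that table compares differently selected patients, so its difference is not an estimate of the treatment effect on depth of response.

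Leaving the denominator unstated is a second problem, because the choice then stays open until the data are seen.

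**Working it through.** **Step 1: which patients make up the planned MRD set.** Section 14.3.4 gives substudy sizes of 600 ("approximately 600 evaluable Phase III patients may participate in this substudy") and 200 ("approximately 200 evaluable Phase II patients may participate in this substudy"). Count = substudy size × CR/CRi rate × sample rate:
- Phase III basis: 600 × 0.60 × 0.90 = 324 marrow; 600 × 0.60 × 0.95 = 342 blood.
- Phase II basis: 200 × 0.60 × 0.90 = 108 marrow; 200 × 0.60 × 0.95 = 114 blood.

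All four match the stated counts, so the planned MRD set holds CR/CRi patients only.

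**Step 2: inputs for the arm comparison.**
- Control CR/CRi 60%: the 14.3.4 assumption, stated there for all patients and used here for the control arm.
- Control MRD-positive rate among responders 25%: 14.3.4.
- Experimental CR/CRi 68%: section 1.3, older newly diagnosed patients given uproleselan with 7+3 (25 patients, uncontrolled, idarubicin as the anthracycline).
- q, the MRD-positive share among the 8 points of added responders: not in the documents, varied from 25% to 100%.
- Patients who would respond on either arm keep the same MRD status (assumption).

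**Step 3: formulas.**
- Responder-only MRD-positive rate, experimental = (0.60 × 0.25 + 0.08 × q) / 0.68 = (0.15 + 0.08q) / 0.68.
- MRD-negative CR/CRi among all randomized, experimental = 0.60 × 0.75 + 0.08 × (1 − q) = 0.45 + 0.08(1 − q).
- Control values: 25.0% and 0.60 × 0.75 = 45.0%.

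| q | MRD-positive among responders, experimental v control | MRD-negative CR/CRi among all randomized, experimental v control |
|---|---|---|
| 25% | 0.17/0.68 = 25.0% v 25.0% | 51.0% v 45.0% |
| 50% | 0.19/0.68 = 27.9% v 25.0% | 49.0% v 45.0% |
| 75% | 0.21/0.68 = 30.9% v 25.0% | 47.0% v 45.0% |
| 100% | 0.23/0.68 = 33.8% v 25.0% | 45.0% v 45.0% |

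For q above 25% the two measures part. The responder table looks worse on uproleselan, while the all-randomized measure is better or equal. With experimental CR/CRi at 65%, the responder-only rate runs from 26.9% to 30.8% as q goes from 50% to 100%; at 70% it runs from 28.6% to 35.7%.

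**Step 4: chance of a falsely significant result against uproleselan.** This uses normal-approximation power for two proportions, 90% sampled in each arm, and two-sided 0.05 (assumed, since no level is stated for this test). On the Phase II basis the arms hold 100 × 0.60 × 0.90 = 54 and 100 × 0.68 × 0.90 = 61 marrows. For q of 50%, 75% and 100% the chance is 5%, 10% and 18%, against a nominal 2.5% in that direction. On the Phase III basis it would have been 9%, 23% and 43%. Amendment 04 ended accrual, so the Phase II figures are the relevant ones.

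**The case against.** The strongest reply is that the restriction to responders is inferred. It is explicit only for the MRD and relapse-free survival objective, where remission is needed by definition, and the counts of 324 and 342 serve that power calculation. If every sampled end-of-induction marrow entered the table, patients with resistant disease would count as MRD-positive and most of the artefact would go. This stands in part. A reader might infer that the plan prescribes a responder-only test; it does not, and responder-only is the likely reading because no other MRD population is described. Using all sampled marrows would not restore the randomized comparison either, since patients who die in induction give no sample, and section 1.1 puts early mortality at up to 20%.

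A second reply is that nothing in the documents puts q above 25%, and at 25% there is no distortion. The drug's rationale is greater chemosensitivity, so it may also convert some existing responders to MRD-negative, which would offset the shift. Both points are correct. A reader might infer that uproleselan will look worse on MRD; the documents support only that it can. Larger gaps are also easy to produce. A 55% control rate, the middle of the 50-60% in section 1.1, with 65% on the experimental arm and q = 100%, gives (0.1375 + 0.10)/0.65 = 36.5% v 25.0%. That replaces the substudy's own 60% and takes the extreme value of q.

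A third reply concerns weight. The objectives in 14.3.2 are headed exploratory, and none of the four is an MRD comparison by arm. The Phase II version is called hypothesis-generating. CR/CRi by regimen is a planned secondary result, and EFS counts induction failure as an event. This stands. A reader might infer that a real gain would stay hidden, but added remissions would be visible next to the MRD table. MRD among remitters is also a fair descriptive question.

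**Conclusion.** The point holds as a matter of estimand and denominator in an exploratory analysis. As written, 14.3.4 most likely tests a between-arm difference within a group selected by treatment response. With CR/CRi of 60% v 68% and existing responders unchanged, the artefact in the responder-only MRD-positive rate is 0 to 8.8 points (33.8 − 25.0) as q goes from 25% to 100%, while MRD-negative CR/CRi among all randomized is 0 to 6 points better on the experimental arm. The direction rests on q exceeding 25%, which is an assumption, and the 68% comes from a small uncontrolled cohort.

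With about 108 marrow samples, the main concern is a biased estimate; a falsely significant result is less likely. The EFS and OS analyses are not affected, and the documents give no ground for reading this as a threat to the trial's main conclusions. It is still worth correcting before the data are analyzed, because a better comparison can be made from data already collected.

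**What to change.** In 14.3.4, replace the arm-comparison sentence with a stated estimand: the proportion with MRD-negative CR/CRi at end of induction among all randomized patients registered to LC1, compared between arms as randomized. Count non-remission and death as not achieved. Treat CR/CRi without an MRD sample as missing, and report a best-case and worst-case range. Because LC1 registration coincides with trial registration, this set is fixed at registration and keeps the randomized comparison.

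Keep the MRD rate among responders, and any end-of-consolidation rate, as a descriptive table labelled as not a randomized comparison. The end-of-consolidation group is selected further still.

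The cost is a short change of wording and one extra table, with no new samples. There are two small downsides. The endpoint partly overlaps the CR/CRi rate already planned. The missing-sample range is also not negligible: with marrow from 90% of responders, unsampled remissions are 0.10 × 60% = 6.0% of all patients on control and 0.10 × 68% = 6.8% on the experimental arm in the scenario above. That is as large as the differences in question, so the range should be shown beside the estimate.

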## 15.0 MONITORING PLAN AND REGULATORY CONSIDERATIONS

### 15.1 Central Data Monitoring and Source Data Verification

Centralized data monitoring activities will be performed for all patient cases enrolled at each site (as identified by a unique CTEP Institution Code). The cases selected for central data monitoring will be reviewed for completeness and consistency via source data verification (SDV) with source documents compared to the data reported via the electronic Case Report Forms in Rave. Central data monitoring with SDV will be performed for all patients for *key eligibility and response/disease outcomes*. The first two treatment cycles will be reviewed for all patients.

A source document is a document in which data collected for a clinical trial is first recorded. A subset of data is usually later entered in the Case Report Forms. The ICH-GCP guidelines define source documents as original documents, data, and records.

The following data and documents will be reviewed via centralized data monitoring and source documents should be uploaded within the two weeks after registration:

- 1) **Informed Consent Document (ICD):** De-identified last page of the signed and dated informed consent document as well as any pages with responses indicated by patient for optional studies. Patient's full signature should be redacted, but date should be retained.
- 2) **Key Eligibility Criteria:**
  - a. Diagnosis of AML based on 2017 WHO criteria excluding acute promyelocytic leukemia with PML-RARA
  - b. No activating mutation in Fms-like tyrosine kinase-3 (FLT3)
  - c. No evidence of CNS involvement of AML
  - d. No prior chemotherapy for MDS or AML including hypomethylating agents or lenalidomide (see section 3.3.2 for exceptions).
  - e. Age  $\geq 60$  years
- 3) **Treatment Verification/IP Administration:** Applicable drug administration and dosing records to document the first cycle of induction therapy and the first cycle of consolidation therapy.

4) **Disease Outcome/Response:** Verify the claimed response for the primary endpoint based on source data containing assessment or response per the Revised Recommendations of the International Working Group for Diagnosis, Standardization of Response Criteria, Treatment Outcomes, and Reporting Standards for Therapeutic Trials in Acute Myeloid Leukemia.

See the *Data Submission Schedule*, available on the Alliance and CTSU websites, for additional details regarding source data verification requirements.

Sites should ensure that patient identifiers have been removed from all pages that will be uploaded and add study-specific identifying information (i.e. Alliance Patient ID) and then scan and upload all source documents to Rave. Please ensure that all pages are legible and correct.

In the event central monitoring or review of key performance indicators (KPIs) identify deficiencies, then additional central monitoring, an unscheduled on-site monitoring visit, or an audit visit may be triggered. Deficiencies or KPIs that may elicit one of these responses include, but are not limited to:

- Accrual rate
- Eligibility
- Early Termination
- Data submission timelines
- Outstanding forms
- Outstanding queries
- Query responsiveness
- Protocol deviations

## 15.2 On-site Monitoring

Member networks that accrue five or more patients will be monitored approximately every 12 months. Member networks that accrue 10 or more patients per year will be monitored approximately every 6 months. Member networks that accrue less than five patients will not be monitored on site, unless other deficiencies have been identified, and thus indicate the need for a monitoring visit.

The first on-site monitoring visit will occur after the fifth patient has been enrolled and within 6 months of the fifth enrollment. Thereafter, on-site monitoring visits will occur at approximately 12 month intervals during the treatment phase of the study.

At the end of each on-site monitoring visit, the monitor will debrief the site study team and highlight areas that need improvement (if applicable). Any deficiencies and related actions will be documented in a visit follow-up letter, and on-site monitoring visit follow-up letters will be distributed to the site Principal Investigator (PI) and Lead Clinical Research Professional within 30 days of the last day of the on-site monitoring visit.

All affiliate/component sites will be monitored at the main member site during scheduled on-site visits, unless a separate on-site visit is deemed necessary. All records from affiliate/component sites must be accessible to monitors. Institutions that utilize electronic medical records must provide monitors access to electronic records.

Routine monitoring visits will be scheduled at approximately 6 – 12 month intervals, depending on accrual and other KPIs to ensure proper oversight of trial execution. Frequency of monitoring visits may be adjusted and will be determined based upon factors such as enrollment rate, data

quality, protocol compliance, site performance, and the available amount of data to be monitored.

On-site monitoring visits will only be conducted during the treatment phase. Central data monitoring will continue during the follow-up phase. Institutions may also be audited per the Alliance auditing schedule.

Deficiencies impacting the protection of rights and safety of human patients, unreported or underreported safety information, or other non-compliance may result in an increase in the percentage of patient data monitored or monitoring visit frequency.

At selected sites, a minimum 25% of patients will be selected for on-site SDV of the following:

- Eligibility
- Primary endpoint

At selected sites, 100% of patients will be selected for on-site SDV of the following:

- Informed consent

### **15.3 Early Study Closure at Sites**

Institutions may not close this trial without discussion and approval by the Alliance Regulatory team ([[contact]](mailto:[contact])). Before contacting the Alliance regulatory team please confirm this study does not appear on the list of trials terminated by the Alliance or on a study-specific termination memo (located on the “Study Terminations of Patient Follow-up” page of the Alliance website or on the study specific page of the CTSU website).

**APPENDIX I LIST OF SPECIFIC ABNORMALITIES FOR WHICH KARYOTYPES MUST BE PROVIDED FOR SINGLE CELLS**

1. Acute Myeloid Leukemia (AML) and Myelodysplastic Syndromes (MDS)
  - a. any abnormality of 5q
  - b. any abnormality of 7q
  - c. any abnormality of 11q
  - d. +8
  - e. t(8;21)(q22;q22) + missing sex chromosomes
  - f. t(15;17)(q22;q11-12)
  - g. t(9;11)(p22;q23)
  - h. t(6;9)(p23;q34)
  - i. del(16)(q22), inv(16)(p13q22) or t(16;16)(p13;q22)
  - j. Philadelphia chromosome
  - k. ring chromosomes
  - l. any abnormality involving 3q
  - m. any abnormality of 12p
  - n. der (1)t(1;7)(p11;p11)
  - o. any abnormality of 9q
  - p. any abnormality of 17p
  - q. any abnormality of 20q
  - r. any structural abnormality, other than the aforementioned, that is known to be recurrent in AML or MDS.
2. Acute Lymphocytic Leukemia (ALL)
  - a. hyperdiploid cells, especially > 50 chromosomes
  - b. t(4;11)(q21;q23)
  - c. t(8;14)(q24;q32)
  - d. t(2;8)(p11-13;q24)
  - e. t(8;22)(q24;q11)
  - f. Philadelphia chromosome
  - g. t(1;19)(q23;p13) or der(19)t(1;19)(q23;p13)
  - h. t(11;14)(p13;q13)
  - i. t(11;14)(q13-23;q32)
  - j. near-haploid cells
  - k. any deletion of 6q
  - l. any abnormality of 14q
  - m. any abnormality of 9p
  - n. any abnormality of 12p
  - o. any abnormality of 11q
  - p. any structural abnormality, other than the aforementioned, that is known to be recurrent in ALL.

## APPENDIX II COLLABORATIVE AGREEMENTS LANGUAGE

The agent(s) supplied by CTEP, DCTD, NCI used in this protocol is/are provided to the NCI under a Collaborative Agreement (CRADA, CTA, CSA) between the Pharmaceutical Company(ies) (hereinafter referred to as “Collaborator(s)”) and the NCI Division of Cancer Treatment and Diagnosis. Therefore, the following obligations/guidelines, in addition to the provisions in the “Intellectual Property Option to Collaborator”

([http://ctep.cancer.gov/industryCollaborations2/intellectual\\_property.htm](http://ctep.cancer.gov/industryCollaborations2/intellectual_property.htm)) contained within the terms of award, apply to the use of the Agent(s) in this study:

1. Agent(s) may not be used for any purpose outside the scope of this protocol, nor can Agent(s) be transferred or licensed to any party not participating in the clinical study. Collaborator(s) data for Agent(s) are confidential and proprietary to Collaborator(s) and shall be maintained as such by the investigators. The protocol documents for studies utilizing Agents contain confidential information and should not be shared or distributed without the permission of the NCI. If a copy of this protocol is requested by a patient or patient’s family member participating on the study, the individual should sign a confidentiality agreement. A suitable model agreement can be downloaded from: <http://ctep.cancer.gov>.
2. For a clinical protocol where there is an investigational Agent used in combination with (an)other Agent(s), each the subject of different Collaborative Agreements, the access to and use of data by each Collaborator shall be as follows (data pertaining to such combination use shall hereinafter be referred to as “Multi-Party Data”):
  - a. NCI will provide all Collaborators with prior written notice regarding the existence and nature of any agreements governing their collaboration with NCI, the design of the proposed combination protocol, and the existence of any obligations that would tend to restrict NCI's participation in the proposed combination protocol.
  - b. Each Collaborator shall agree to permit use of the Multi-Party Data from the clinical trial by any other Collaborator solely to the extent necessary to allow said other Collaborator to develop, obtain regulatory approval or commercialize its own Agent.
  - c. Any Collaborator having the right to use the Multi-Party Data from these trials must agree in writing prior to the commencement of the trials that it will use the Multi-Party Data solely for development, regulatory approval, and commercialization of its own Agent.
3. Clinical Trial Data and Results and Raw Data developed under a Collaborative Agreement will be made available to Collaborator(s), the NCI, and the FDA, as appropriate and unless additional disclosure is required by law or court order as described in the IP Option to Collaborator ([http://ctep.cancer.gov/industryCollaborations2/intellectual\\_property.htm](http://ctep.cancer.gov/industryCollaborations2/intellectual_property.htm)). -Additionally, all Clinical Data and Results and Raw Data will be collected, used and disclosed consistent with all applicable federal statutes and regulations for the protection of human subjects, including, if applicable, the *Standards for Privacy of Individually Identifiable Health Information* set forth in 45 C.F.R. Part 164.
4. When a Collaborator wishes to initiate a data request, the request should first be sent to the NCI, who will then notify the appropriate investigators (Group Chair for Cooperative Group studies, or PI for other studies) of Collaborator's wish to contact them.
5. Any data provided to Collaborator(s) for Phase 3 studies must be in accordance with the guidelines and policies of the responsible Data Monitoring Committee (DMC), if there is a DMC for this clinical trial.

6. Any manuscripts reporting the results of this clinical trial must be provided to CTEP by the Group office for Cooperative Group studies or by the principal investigator for non-Cooperative Group studies for immediate delivery to Collaborator(s) for advisory review and comment prior to submission for publication. Collaborator(s) will have 30 days from the date of receipt for review. Collaborator shall have the right to request that publication be delayed for up to an additional 30 days in order to ensure that Collaborator's confidential and proprietary data, in addition to Collaborator(s)'s intellectual property rights, are protected. Copies of abstracts must be provided to CTEP for forwarding to Collaborator(s) for courtesy review as soon as possible and preferably at least three (3) days prior to submission, but in any case, prior to presentation at the meeting or publication in the proceedings. Press releases and other media presentations must also be forwarded to CTEP prior to release. Copies of any manuscript, abstract and/or press release/ media presentation should be sent to:

Email: [[contact]](mailto:[contact])

The Regulatory Affairs Branch will then distribute them to Collaborator(s). No publication, manuscript or other form of public disclosure shall contain any of Collaborator's confidential/ proprietary information.

